6.1 Study treatment

For this study, the term “investigational” refers to LDK378. All dosages prescribed and dispensed to the patient and all dose changes during the study must be recorded on the Dosage Administration Record eCRF.

LDK378 will be provided and supplied by Novartis. LDK378 is supplied as 150 mg hard gelatin capsules as individual open label patient supply. LDK378 will be dosed on a flat scale of 750 mg/day and not be adjusted to body weight or body surface area.

A complete cycle of treatment is defined as 28 days of once daily treatment of LDK378.

6.1.1 Dosing regimen

LDK378 will be administered orally once daily at a dose of 750 mg (five 150 mg capsules) on a continuous dosing schedule. The treatment period will start on Cycle 1 Day 1.

Each study site will be supplied with LDK378 by Novartis. LDK378 is supplied as 150 mg hard gelatin capsules as individual patient supply, packaged in bottles. Medication labels will comply with legal regulation and be printed in local language. The storage conditions for the study treatment will be described on the medication label. LDK378 will be dispensed by the pharmacist or designee at the investigator's institution.

LDK378 will be administered orally once daily at a dose of 750 mg (five 150 mg capsules) on a continuous dosing schedule. The investigator must instruct the patient to take the study drug exactly as prescribed.

The general dose and treatment schedule of the study treatments are listed in [Table 6-1](#).

- Patients should take LDK378 once daily at approximately the same time each day in the morning, afternoon, or evening.
- Patients should take LDK378 on an empty stomach (i.e. fast from food and drink, except water) at least 1 hour before or 2 hours after a light meal. Each dose of LDK378 should be taken with a glass of water and consumed over as short a time as possible (i.e. not slower than 1 capsule every 2 minutes).
- Patients should be instructed to swallow whole capsules and not to chew or open them.
- If vomiting occurs during the course of treatment, no re-dosing of the patient is allowed before the next scheduled dose.

- Patients should be instructed not to make up missed doses or partial doses (i.e. when the entire dose is not taken as instructed). A missed or partial dose will be defined as a case when the full dose is not taken within 8 hours after the approximate time of the usually daily dosing. That day's dose (or part remaining dose) should be omitted and the patient should continue treatment with the next scheduled dose on the following day.

Table 6-1 Dose and treatment schedule

Study treatments	Pharmaceutical form and route of administration	Dose	Frequency and/or Regimen
LDK378	Gelatin capsule for oral use	750 mg (5 x 150 mg / capsule)	Once daily (28 day / cycle)

6.1.2 Guidelines for continuation of treatment

For guidelines for dose modification of treatment, refer to [Section 6.3](#).

6.1.3 Treatment duration

Patients will continue LDK378 until they experience any of the following:

- Disease progression (radiologically documented according to RECIST 1.1 by the investigator). LDK378 therapy will continue until progressive disease if clinically acceptable. However, LDK378 may be continued beyond RECIST-defined progressive disease (PD) as assessed by the investigator, if in the judgment of the investigator, there may be clinical benefit with continued treatment.
- Unacceptable toxicity that precludes further treatment
- Start of a new anti-cancer therapy
- Pregnancy
- Treatment is discontinued at the discretion of the investigator or patient
- Lost to follow-up
- Death
- Study terminated by Sponsor

Patients who permanently discontinue the study drug for any reason other than disease progression must, if agreeing to further follow-up, continue efficacy assessments as scheduled in the protocol until the time of confirmed disease progression.

6.1.4 Definition of treatment cycle

A treatment cycle is defined as 28 calendar days from the start of treatment with LDK378 (Day 1, Cycle 1) for the purposes of scheduling procedures and evaluations.

6.2 Dose escalation guidelines

Not applicable to this study

6.3 Dose modifications

6.3.1 Dose modification and dose delay

For patients who do not tolerate the protocol-specified dosing schedule, dose adjustments are permitted in order to allow the patients to continue the study treatment. Any changes in LDK378 must be recorded on the Dosage Administration Record eCRF.

General guidelines for dose modifications for toxicities other than those listed in [Table 6-3](#).

For grade 1 and tolerable grade 2 treatment-related toxicities, patients are encouraged to continue at the current dose of study treatment. For intolerable grade 2 treatment-related toxicities, dosing should be interrupted until resolution to grade 1 or lower followed by dose reduction to the next dose level. For grade 3 or grade 4 treatment-related toxicity that is not considered by the investigator to be life-threatening, patients should interrupt study treatment until resolution to grade 1 or lower; then study treatment may continue following a dose reduction to the next dose level, if in the opinion of the Investigator, the patient continues to experience clinical benefit and after discussion with the Sponsor. For any grade 3 or 4 treatment-related toxicity that is considered by the investigator to be life-threatening, permanently discontinue study treatment.

More detailed LDK378 modification guidelines are described in [Section 6.3.3](#) and [Table 6-3](#) selected toxicities.

All dose modifications, interruptions or discontinuations must be based on the worst preceding toxicity as graded by the NCI Clinical Toxicity Criteria (NCI-CTCAE) version 4.03. Patients whose treatment is interrupted or permanently discontinued due to an AE must be followed until resolution or stabilization of the event. Patients requiring interruptions greater than 28 consecutive days will be discontinued from study treatment. In certain cases, if the Investigator and the Sponsor conclude that a patient, who has experienced a treatment interruption greater than 28 consecutive days, could benefit from additional treatment, continuation may be allowed.

6.3.2 Treatment interruption and treatment discontinuation

If the administration of LDK378 is temporarily interrupted for reasons other than toxicity, then treatment with LDK378 may be resumed at the same dose. The same applies if the patient experiences an unacceptable toxicity not specifically described in [Table 6-3](#), provided this toxicity resolved to \leq CTCAE grade 1.

If the treatment with LDK378 is withheld due to toxicity, scheduled visits and all assessments should continue to be performed (with the exception of the dosing of the withheld study drug), as described in [Table 7-1](#).

If the treatment with LDK378 dosing is withheld for more than 28 consecutive days (counting from the first day when a dose was missed), due to treatment-related toxicity, then LDK378 should be permanently discontinued except in cases where the investigator believes the patient continues to derive clinical benefit. In such cases, treatment with LDK378 may be resumed at a lower dose.

Detailed guidelines for follow-up of study drug related AE or an abnormal laboratory value must be followed as described in [Section 6.3.4](#).

All patients will be followed for safety until 30 days after the last dose of LDK378. Patients whose treatment is temporarily interrupted or permanently discontinued due to an AE or abnormal laboratory value must be followed until resolution or stabilization of the event, whichever comes first, including all study assessments appropriate to monitor the event.

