6.3.3 Criteria for LDK378 dose modifications

LDK378 dose reduction will follow the dose reduction steps described in [Table 6-2](#). For each patient, a maximum of 3 dose modifications is allowed after which the patient must be discontinued from treatment with LDK378. Once the dose of LDK378 has been reduced, it cannot be re-escalated. If a patient continues treatment with LDK378 after RECIST-defined PD as determined by the investigator, the criteria for dose modification will also apply.

Table 6-2 Dose reduction steps for LDK378

LDK378 dose levels	Dose* and schedule
Starting dose level	750 mg qd continuously
Dose level – 1	600 mg qd continuously
Dose level – 2	450 mg qd continuously
Dose level – 3	300 mg qd continuously **

*Dose reduction should be based on the worst preceding toxicity as per NCI-CTCAE version 4.03.

**Dose reduction below 300 mg/day is not allowed. If a dose reduction below 300 mg/day is required, the patient should be permanently discontinued from LDK378

Guidelines for dose interruptions and re-initiation of LDK378 treatment (with or without dose reduction) are described in [Table 6-3](#).

Table 6-3 Criteria for interruption and re-initiation of LDK378 treatment

Worst toxicity (CTCAE 4.03 Grade)*	Dose Modifications for LDK378
HEMATOLOGICAL	
Neutropenia (ANC: Absolute neutrophil count)	
Grade 1 (ANC < LLN - $1.5 \times 10^9/L$)	Maintain dose level
Grade 2 (ANC < 1.5 and $\geq 1.0 \times 10^9/L$)	
Grade 3 (ANC < 1.0 and $\geq 0.5 \times 10^9/L$)	
Grade 4 (ANC < $0.5 \times 10^9/L$)	Omit dose until resolved to \leq Grade 2, then: If resolved in \leq 7 days, then maintain dose level If resolved in $>$ 7 days, then \downarrow 1 dose level
Febrile neutropenia (ANC < $1.0 \times 10^9/L$, with a single temperature of $\geq 38.3^{\circ}C$ or a sustained temperature of $\geq 38^{\circ}C$ for more than one hour)	Omit dose until clinically resolved and neutropenia \leq Grade 2, then \downarrow 1 dose level
Thrombocytopenia	
Grade 1 (PLT < LLN - $75 \times 10^9/L$)	Maintain dose level
Grade 2 (PLT < 75 and $\geq 50 \times 10^9/L$)	
Grade 3 (PLT < 50 and $\geq 25 \times 10^9/L$)	Omit dose until resolved to \leq Grade 2, then: If resolved in \leq 7 days, then maintain dose level If resolved in $>$ 7 days, then \downarrow 1 dose level
Grade 4 (PLT < $25 \times 10^9/L$)	Omit dose until resolved to \leq Grade 2, then \downarrow 1 dose level
HEPATIC	
Alkaline phosphatase and/or Gamma-glutamyl transpeptidase (GGT)	

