Isolated elevations of any grade	Maintain dose level
Total Bilirubin** (for patients with Gilbert Syndrome these dose modifications apply to changes in direct [conjugated] bilirubin only)	
Grade 1 ($>$ ULN and $\leq 1.5 \times$ ULN)	Maintain dose level with liver function test (LFTs)*** monitored as per protocol

Worst toxicity (CTCAE 4.03 Grade)*	Dose Modifications for LDK378
Grade 2 (> 1.5 and \leq 3.0 x ULN) with ALT or AST \leq 3.0 x ULN	Omit dose until resolved to \leq Grade 1, then: If resolved in \leq 7 days, then maintain dose level If resolved in > 7 days, then \downarrow 1 dose level
Grade 3 (> 3.0 and \leq 10.0 x ULN) with ALT or AST \leq 3.0 x ULN	Omit dose until resolved to \leq Grade 1, then: If resolved in \leq 7 days, \downarrow 1 dose level If resolved in > 7 days discontinue patient from LDK378
Grade 4 (> 10.0 x ULN)	Permanently discontinue patient from LDK378
AST or ALT	
Grade 1 (> ULN and \leq 3.0 x ULN)	Maintain dose level with LFTs*** monitored per protocol
Grade 2 (> 3.0 and \leq 5.0 x ULN) without total bilirubin elevation to > 2.0 x ULN	Maintain dose level with LFTs*** monitored per protocol
Grade 3 (> 5.0 and \leq 20.0 x ULN) without total bilirubin elevation to > 2.0 x ULN	Omit dose until resolved to \leq Grade 1, then \downarrow 1 dose level
Grade 4 (> 20.0 x ULN) without total bilirubin elevation to > 2.0 x ULN	Omit dose until resolved to \leq Grade 1, then \downarrow 1 dose level
AST or ALT and concurrent total bilirubin	
AST or ALT > 3.0 x ULN with total bilirubin > 2.0 x ULN in the absence of cholestasis or hemolysis	Permanently discontinue patient from LDK378 Refer to Section 6.3.4.2 for additional follow-up
PANCREATIC	
Amylase and/or lipase elevations (in the absence of clinical symptoms)	
Grade 1 (> ULN and \leq 1.5 x ULN)	Maintain dose level
Grade 2 (> 1.5 - 2.0 x ULN)	Maintain dose level
Grade \geq 3 (> 2.0 x ULN)	Omit dose until resolved to \leq Grade 1, then \downarrow 1 dose level
Note: Withhold LDK378 for acute onset of new or progressive unexplained abdominal symptoms, such as severe pain or vomiting; perform diagnostic procedures (e.g., abdominal CT scan or ultrasound) to exclude pancreatic pathology.	

Worst toxicity (CTCAE 4.03 Grade)*	Dose Modifications for LDK378
RENAL	
Serum creatinine	
Grade 1 (>1 and ≤ 1.5 x baseline; > ULN and ≤1.5 x ULN)	Maintain dose level

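### For treatment-related toxicity outside Table 6-3, Sections 6.3.1 and 6.3.2 give different restart doses, and Table 6-3 treats one combined bilirubin and transaminase elevation more leniently than a milder one

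*Protocol*

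**What the plan says.** Protocol Section 6.3.1 introduces its rule as "General guidelines for dose modifications for toxicities other than those listed in" Table 6-3, and grades it by treatment-related toxicity:

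- Intolerable grade 2: "dosing should be interrupted until resolution to grade 1 or lower followed by dose reduction to the next dose level".
- Grade 3 or 4, not life-threatening: interrupt to grade 1 or lower, "then study treatment may continue following a dose reduction to the next dose level", provided there is clinical benefit and the sponsor has been consulted.
- Grade 3 or 4 "that is considered by the investigator to be life-threatening, permanently discontinue study treatment".

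Section 6.3.2 first allows restart at an unchanged dose when the interruption was not for toxicity. It then continues: "The same applies if the patient experiences an unacceptable toxicity not specifically described in" Table 6-3, on the sole condition that the toxicity has come down to grade 1 or lower.

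In Table 6-3 the grade 2 and grade 3 bilirubin rows carry an enzyme condition, "3.0 x ULN) with ALT or AST" at or below 3.0 x ULN. The grade 2 to 4 AST/ALT rows apply only if bilirubin has not risen above 2.0 x ULN. The combined row (AST or ALT above 3.0 with bilirubin above 2.0 x ULN) requires permanent discontinuation, but only without cholestasis or hemolysis. Section 6.3.4.2 orders discontinuation at its liver-injury thresholds when cholestasis is absent and does not exempt hemolysis.

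**The concern.** Both sections act on the same patient at the same moment, when a toxicity outside Table 6-3 has resolved to grade 1 or lower, and they name different doses. A site following 6.3.2 can return a patient to full dose after a severe treatment-related event where 6.3.1 would allow only a lower dose. The choice lasts: "Once the dose of LDK378 has been reduced, it cannot be re-escalated" (Section 6.3.3), and the same section allows three modifications before treatment must stop. Section 12 permits no authorized deviations, yet a site cannot tell which text it would be deviating from.

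In the hepatic rows, the enzyme condition can switch off the bilirubin instruction just when the enzymes are also raised, leaving a more lenient instruction for the worse liver panel or none at all.

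**Working it through.** **Restart dose, side by side (treatment-related, not in Table 6-3, resolved to grade 1 or lower)**

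| Event | 6.3.1 | 6.3.2 |
|---|---|---|
| Intolerable grade 2 | One level lower | Same dose allowed |
| Grade 3/4, not life-threatening | One level lower, with clinical benefit and sponsor discussion | Same dose allowed |
| Grade 3/4, life-threatening | Permanent stop | Not reached: there is no temporary interruption to end |

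Two features of 6.3.2 tell against reading it as confined to unrelated toxicity. Its own 28-day rule is expressly limited to treatment-related toxicity, while the disputed sentence has no such limit. And an unacceptable toxicity that must come down to grade 1 was at least grade 2, the range that 6.3.1 governs.

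Such events exist: in Table 1-1, anemia (13/255 = 5.1%) and hypokalemia (11/255 = 4.3%) occurred at grade 3/4, and neither has a row in Table 6-3. Those counts are regardless of cause, so they do not give the number in dispute.

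**Table 6-3 hepatic rows on a grid**

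Inputs, in multiples of ULN: bilirubin 0.8, 1.2, 1.8, 2.5, 4, 12; ALT and AST each 0.8, 2, 4, 6, 25; cholestasis or hemolysis yes or no. That is 6 x 5 x 5 x 2 = 300 cells, less 2 entirely normal = 298. Where several rows match, the strictest is taken. An inversion is a cell whose action is less strict than that of a cell with the same cholestasis/hemolysis status and equal or lower values. The counts test the wording; they are not frequencies.

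Reading the enzyme condition literally (either enzyme at or below 3.0 is enough):

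- No row: 2 bilirubin values (2.5, 4) x 3 ALT x 3 AST values (4, 6, 25), cholestasis or hemolysis present = 18 cells.
- Inversions: 10 further cells. Two are bilirubin 1.8 with ALT 4 and AST 4, with and without cholestasis or hemolysis. The other eight are bilirubin 2.5 with one enzyme at 6 or 25 and the other at 0.8 or 2, cholestasis or hemolysis present (2 x 2 x 2 orderings = 8).

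Reading the condition as both enzymes at or below 3.0 gives 42 no-row cells and 10 inversions, so the problem does not depend on the reading.

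Individual cells (bilirubin/ALT/AST):

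- 1.8/2/2: grade 2 bilirubin row, omit dose. 1.8/4/4: only the grade 2 AST/ALT row, maintain dose.
- 2.5/4/4 with ALP 2.5 and no bone metastasis: R = 4/2.5 = 1.6, below 2 with ALP above 2.0, so cholestasis under 6.3.4.2. The combined row is excluded, as are both bilirubin rows and the AST/ALT row. No row applies.
- Footnote ** rescues only purely indirect grade 3 or 4 bilirubin with hemolysis ruled out.

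**Effect on the reported data**

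One patient handled differently changes the dose-reduction rate by 1/20 = 5 percentage points. As an illustration only, assume one 7-day interruption from day 29 of 168, leaving 133 dosing days:

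- Same dose: (28 x 750 + 133 x 750)/(168 x 750) = 95.8% relative dose intensity.
- One level lower: (28 x 750 + 133 x 600)/(168 x 750) = 80.0%.

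**The case against.** The best defence is that the specific rule beats the general one. Section 6.3.1 is graded and limited to treatment-related toxicity; 6.3.2 is permissive. Read that way, 6.3.2 is left with unrelated toxicity and nothing conflicts. This is sensible and is what the fix adopts, but the protocol states no precedence. The wording of 6.3.1 is also softer than a strict requirement, since it is offered as general guidelines. Even so, it makes a reduction the condition for resuming, which same-dose restart does not satisfy.

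Nor does the rule "All dose modifications, interruptions or discontinuations must be based on the worst preceding toxicity" settle the hepatic inversion. At 1.8/4/4 both abnormalities are grade 2, and the bilirubin row is excluded by its own enzyme condition.

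For the no-row cells, one can argue that 6.3.1 applies as a fallback and already yields interruption and reduction. But 6.3.1 is written for toxicities not listed in Table 6-3, while bilirubin and transaminases are listed. If the fallback is accepted, the reader meets the conflict with 6.3.2 again.

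Safeguards limit the hepatic risk: at least weekly liver tests from grade 2 and medical review for cholestasis (6.3.4.2), and the investigator's duty to stop if continuing would harm the patient (7.1.3). They do not set the dose. It also stands that the action for cholestatic or hemolytic patients is partly a clinical choice.

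Stronger inferences are tempting and should not be drawn:

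- That 6.3.2 permits rechallenge after a life-threatening related event. Sections 6.3.1 and 7.1.3 require discontinuation.
- That the 28-day rules in the two sections conflict. Both can be followed.
- That the grid shows 28 inversions. That adds the 18 no-row cells, which have no action to be less strict, to the 10 real ones.
- That Table 1-1 bounds the frequency. It lists only terms with at least 10% all-grade incidence, regardless of cause, and Section 8.1 counts laboratory abnormalities as adverse events only under conditions, so adverse-event rates do not cap bilirubin elevations.

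**Conclusion.** The conflict over the restart dose is real and should be fixed. It covers treatment-related toxicity outside Table 6-3 at intolerable grade 2 and at non-life-threatening grade 3 or 4. The hepatic inversion at bilirubin above 1.5 to 2.0 with both enzymes above 3 to 5 x ULN is also real. The no-row cells (bilirubin above 2 to 10 with both enzymes above 3 x ULN and cholestasis or hemolysis, apart from footnote **) and the disagreement between Table 6-3 and 6.3.4.2 on hemolysis without cholestasis are secondary.

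The main consequence is for patient safety and consistent dosing across sites. The number of patients affected cannot be bounded from the documents. A reader might infer that the tolerability endpoint as a whole is compromised. It is not: both paths begin with an interruption, so the patient counts under Protocol 10.5.3.5 either way. Only the separate dose-reduction tally and dose intensity (SAP 2.6) differ. ORR, its confidence interval and the sample size are unaffected. The relative dose intensity contrast rests on an assumed interruption and shows scale only.

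**What to change.** 1. Section 6.3.2: keep the second sentence but limit it to toxicity that is not treatment-related, and state that 6.3.1 governs treatment-related toxicity, including permanent discontinuation if life-threatening.
2. Table 6-3: apply the grade 2 bilirubin action also when bilirubin is above 1.5 to 2.0 and both enzymes are above 3 to 5 x ULN, and state that the stricter action stands when rows overlap.
3. For bilirubin above 2 to 10 with both enzymes above 3 x ULN and cholestasis or hemolysis, the sponsor should assign an action, at least omitting the dose, and state whether Table 6-3 or 6.3.4.2 governs hemolysis without cholestasis. The exact choice is clinical.

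One way to do items 2 and 3 together is to replace the enzyme condition in the grade 2 and 3 bilirubin rows, and the bilirubin condition in the grade 2 to 4 AST/ALT rows, with an exception for cases meeting the permanent-discontinuation row. With the stricter-action rule, the grid then shows no empty cells and no inversions, including the eight cells at bilirubin 2.5. The existing handling of Gilbert syndrome should stay.

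The cost is one amendment to one sentence and up to five table rows, with no added visits, tests or patients. The downside of that broader rewrite is that some cholestatic or hemolytic patients will have doses omitted or reduced, or will be discontinued under the grade 3 bilirubin 7-day rule, where the table is now silent.

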4.1.2.2 End of Treatment (EOT)

When the patient discontinues from study treatment, End of Treatment (EOT) visit must be performed as soon as possible and within 7 days of the last dose of LDK378. Patients will be contacted for the safety follow-up 30 days after their last dose of LDK378 to determine if they have experienced any new AEs and/or to follow resolution of ongoing AEs.

Following the cessation of tumor follow-up assessments, patients will be contacted every 3 months to assess patient survival status and/or whether the patient started any other antineoplastic therapies since discontinuing study treatment. Patients do not need to visit the clinic during the survival follow-up.

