7.1 Study flow and visit schedule

Table 7-1 lists all of the assessments and indicates with an “X” the visits when they are performed. Each treatment cycle is 28 days (the 28 days cycle length is fixed regardless of whether the dose of LDK378 is withheld). All visits are to be scheduled according to the appropriate number of calendar days from Cycle 1 Day 1 of study drug administration. A visit window of +/- 1 day in Cycle 1 and +/- 3 days in Cycle 2 onwards is allowed. Imaging evaluations may be performed +/-7 days of the due date of the assessment.

Note: If treatment with LDK378 is withheld at any time during the study, all study visits, safety and efficacy assessments should continue according to the appropriate number of calendar days from Cycle 1 Day 1 as per the schedule of assessments.

All data obtained from these assessments must be supported in the patients’ source documentation. No eCRF will be used as a source document. The table indicates which assessments produce data to be entered into the database (D) or remain in the source documents only (S).

Visit name	Category	Protocol Section	Screening Phase	Treatment Phase				Post treatment follow up phase			Survival follow-up phase
				Cycle 1 (28 d)		Subsequent cycles (28 d)	End of study Treatment (EOT)	30-day safety follow-up	Tumor follow- up if no PD at the EOT	Study phase completion	
Screening Visit (Day -28 to Day -1)				Cycle 1 Day 1	Cycle 1 Day 15	Day 1	End of treatment visit				
Antineoplastic therapies since discontinuation of study treatment	D	7.1.5.3.						X	X		X Every 12 weeks
Survival assessment	D	7.1.5.3.									X Every 12 weeks

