Patients who discontinue study treatment during the treatment phase should be scheduled for a visit as soon as possible and within 7 days after the last dose of study treatment, at which time all of the assessments listed for the EOT visit will be performed. If a patient withdraws from treatment at a study visit, EOT assessments do not need to be repeated. An End of Treatment Phase Disposition eCRF page should be completed, giving the date and reason for stopping LDK378 treatment.

At a minimum, all patients who discontinue study treatment, including those who refuse to return for a final visit, will be contacted for safety evaluations during the 30 days following the last dose of study treatment.

If patients refuse to return for these visits or are unable to do so, every effort should be made to contact them or a knowledgeable informant by telephone to determine the survival status.

Patients who discontinue study treatment should be considered withdrawn from the study after the final visit assessments are performed or when it is clear that the patient will not return for these assessments.

If a patient discontinues study treatment, but continues study assessments, (e.g. during post treatment follow up phase as detailed in [Table 7-1](#)), the patient remains on study until such time as he/she completes protocol criteria for ending study assessments. At that time, the reason for study completion should be recorded on the End of Post Treatment Phase Disposition (Study Phase Completion) eCRF page.

Patients who discontinue study treatment should enter the survival follow-up period or continue tumor assessments when appropriate. Tumor assessments will continue until

progression of disease (radiological as assessed by investigator), patient withdraws consent from tumor assessments, patient is lost to follow-up, death or study terminated by Sponsor.

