11.9 Financial disclosures

Financial disclosures should be provided by study personnel who are directly involved in the treatment or evaluation of patients at the site - prior to study start.

12 Protocol adherence

Investigators ascertain they will apply due diligence to avoid protocol deviations. Under no circumstances should the investigator contact Novartis or its agents, if any, monitoring the study to request approval of a protocol deviation, as no authorized deviations are permitted. If the investigator feels a protocol deviation would improve the conduct of the study this must be considered a protocol amendment, and unless such an amendment is agreed upon by Novartis and approved by the IRB/IEC/REB it cannot be implemented. All significant protocol deviations will be recorded and reported in the CSR.

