2.4 Protocol deviations

Frequency counts and percentages of patients in the FAS with any CSR-reportable protocol deviations (related to study inclusion/exclusion criteria, conduct of the trial, patient management or patient assessment) will be tabulated by the deviation category. All protocol deviations will be listed for the FAS.

The full list of potential CSR-reportable protocol deviations is documented separately in the Study Specification Document (SSD). All protocol deviations will be reviewed during the study and finalized before database lock.

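### For a toxicity hold of more than 28 days, 6.3.1 and 6.3.2 disagree on who may approve a restart, and a patient stopped because the hold passed 28 days cannot meet the 7-day EOT window

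*Protocol*

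**What the plan says.** **Restart.** Protocol 6.3.1 discontinues patients who need interruptions of more than 28 consecutive days, whatever the cause. It permits continuation by exception, on a joint judgement: "if the Investigator and the Sponsor conclude that a patient, who has experienced a treatment interruption greater than 28 consecutive days" stands to gain from further dosing. Protocol 6.3.2 covers holds of the same length due to treatment-related toxicity, counted from the first missed dose. There, "LDK378 should be permanently discontinued except in cases where the investigator believes the patient continues to derive clinical benefit", and dosing may then resume at a lower dose. This sentence gives the Sponsor no role.

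**EOT visit.** Protocol 4.1.2.2 says the EOT "visit must be performed as soon as possible and within 7 days of the last dose of LDK378". Protocol 7.1.3 says patients who discontinue "should be scheduled for a visit as soon as possible and within 7 days after the last dose of study treatment". Appendix 2, section 15.1.30, repeats the 7-day limit. For a patient who withdraws from treatment at a study visit, 7.1.3 adds that "EOT assessments do not need to be repeated". None of these sections makes an exception for a discontinuation decided after a hold.

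**The concern.** Restarting a drug after a month-long toxicity hold is a patient-safety decision, and two adjacent sections give sites different rules for who takes it. A site that reads 6.3.2 alone can restart a patient in good faith and break 6.3.1. The EOT rule has a different fault: for one group of patients, applying the stopping rule correctly guarantees a missed visit window, because the window closes before the rule can take effect.

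**Working it through.** The plan states no figure for this point, so there is none to reproduce. The check compares the two rules and counts days.

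**1. Do the two restart rules cover the same patients?** The 28-day sentence in 6.3.1 is not limited by cause. The one in 6.3.2 is limited to treatment-related toxicity. Every patient under 6.3.2 is therefore also under 6.3.1.

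**2. Is there a rule of precedence?** None is stated. Protocol 7.1.3 requires discontinuation for adverse events as set out in Section 6.3, and that section contains both rules.

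**3. What follows for each kind of restart (hold over 28 days, treatment-related toxicity, lower dose)?**

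| Restart agreed by | Under 6.3.1 | Under 6.3.2 |
|---|---|---|
| Investigator and Sponsor | complies | complies |
| Investigator alone | breach | complies |

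The sections diverge in the second row only.

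**4. Day count for the EOT visit.**
- Last dose = day 0. First missed dose = day 1, where 6.3.2 starts its count.
- By day d, d doses have been missed. More than 28 is first reached at d = 29.
- EOT limit (4.1.2.2, 7.1.3, Appendix 2) = day 7.
- Minimum lateness = 29 − 7 = 22 days.

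The relief in 7.1.3 avoids repeating assessments but does not move the window: a study visit at which the patient is stopped under this rule is itself on day 29 or later.

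**5. What if the window ran from the decision?** For a decision on day 29, it would be day 29 to day 29 + 7 = 36, which is 8 calendar days. SAP 2.8.2 ends the on-treatment period 30 days after the last dose. Days 29 and 30 fall inside it, and days 31 to 36 (6 of the 8) fall after it.

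**The case against.** **On the restart rule**, the best reply is that this is an ambiguity with a compliant path. Section 6.3.2 does not waive Sponsor agreement. It can be read as adding conditions for the toxicity subset, and a site that seeks joint agreement satisfies both sections. Section 6.3.1 also asks for discussion with the Sponsor before restart after non-life-threatening grade 3 or 4 related toxicity outside Table 6-3, so some of these patients already bring Sponsor contact. All of this is true and keeps the point small. It does not remove it: discussion is not agreement, and the text of 6.3.2 makes the investigator's belief sufficient.

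**On the EOT visit**, little is lost. Under 6.3.2 and 7.1, visits and assessments continue while drug is withheld. The list of CSR-reportable deviations is in a separate specification document (SAP 2.4), so whether the miss would be reported is unknown. Section 6.3.1 speaks of patients requiring a long interruption, so a decision to stop can come before day 29. That stands: the 22-day figure applies only to patients stopped because the hold has passed 28 days.

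A reader might shorten the miss by adding the general visit window: "A visit window of +/- 1 day in Cycle 1 and +/- 3 days in Cycle 2 onwards is allowed". The documents do not support this. Those windows belong to visits scheduled by calendar days from Cycle 1 Day 1, whereas the EOT visit is tied to the last dose.

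**Conclusion.** Both parts are wrong as written and minor. The restart conflict is the main one, because it concerns a safety decision. The EOT conflict is certain on the day count (at least 22 days late) but costs little data. Sample size, ORR and its confidence interval are unaffected.

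The documents give no rate of holds longer than 28 days, so the number of patients affected is unknown and may be 0 of 20. A probability of seeing at least one could be computed from an assumed rate, but it would rest wholly on that assumption. It would also count patients who restart and never face the EOT problem.

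A reader might infer two stronger conclusions that the documents do not support:

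- **The late EOT visit distorts exposure.** SAP 4.9.7 can impute a missing last-dose date from the EOT visit. But a site applying the 28-day count must know the first missed dose, and SAP 4.6 treats interruptions as 0 mg entries in the dosing record. The last non-zero dose is therefore normally identifiable. Substituting for a date that is unavailable also does not contradict the definition of last administration in SAP 2.6.
- **Section 12 leaves a site stranded.** It bars contacting the Sponsor "to request approval of a protocol deviation, as no authorized deviations are permitted". But seeking the Sponsor's conclusion under 6.3.1 is a protocol step, not a request to approve a deviation. Section 12 also provides for significant deviations to be recorded and reported in the CSR.

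**What to change.** **Restart.** In 6.3.2, replace the exception that rests on the investigator's belief with: *unless the Investigator and the Sponsor both conclude, and document before the first restarted dose, that the patient could benefit from additional treatment*. Keep the lower restart dose in 6.3.2 and the 300 mg floor in Table 6-2.

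**EOT visit.** In 4.1.2.2, 7.1.3 and Appendix 2 (15.1.30), add for discontinuations decided during a dose hold only: *the EOT visit takes place within 7 days of the recorded decision to discontinue permanently*. Leave the present rule for all other discontinuations, and keep the 7.1.3 relief from repeating assessments when the decision is made at a study visit.

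**Cost.** The change is wording in four protocol places, through an amendment with IRB approval (Section 12.1), and could travel with the next one. Sites must obtain documented Sponsor agreement before a restart. They must also record a decision date, because Appendix 2 (15.1.25) takes the date of discontinuation from the EOT visit itself. Some EOT visits would coincide with or follow the 30-day safety contact. Results from after the on-treatment period would be listed and flagged rather than tabulated. The SAP needs no change.
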